4.5 Secondary Endpoints

Objective	Endpoints
2	Mental health condition outcomes will be assessed up to two years post-vitiligo diagnosis, including history of prior mental health condition and will comprise of depression (record of any depressive episodes and/or major recurrent depression diagnosis) and anxiety disorders, defined by the International Statistical Classification of Diseases and Related Health Problems 10th Revision (ICD10) classification, and identified using algorithms validated for use in UK primary care data (See previously published codes lists: (4))
3	Other mental health condition outcomes will be assessed up to two years post-vitiligo diagnosis and will comprise of parasuicide/suicide attempts, adjustment disorder and sleep disturbance, defined by the International Statistical Classification of Diseases and Related Health Problems 10th Revision (ICD10) classification, and identified using algorithms validated for use in UK primary care data (See previously published codes lists: (4))

4	Healthcare utilisation outcomes will comprise primary care visits, dermatology referrals, mental health referrals (including but not limited to those via IAPT; Improving Access to Psychological Therapies and psychiatric reviews) in the two years post-vitiligo diagnosis.
5	Unemployment in the two years post-vitiligo diagnosis will be identified using Read codes relating to unemployment recorded in the primary care record or the issuing of IB113 or ESA113 forms (See previously published codes lists: (4)). Time off work in the two years post-vitiligo diagnosis will be indicated by the issuing of Med 3 certification from primary care (Statement of Fitness for Work certification) (See previously published codes lists: (4)).

Table 2: Secondary endpoints.

5. General Study Design and Plan

The study will use retrospectively collected anonymised data from all eligible people contributing to the Optimum Patient Care Research Database (OPCRD)(5) at the date of data extraction. A matched-cohort design will be used for incident (and prevalent) vitiligo related healthcare utilisation, mental health conditions and work impacts. Lifetime risk will be calculated using adapted survival analysis to account for the competing risk of death and will be estimated for the population overall and separately in sociodemographic subgroups of interest.

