8.3 Secondary Endpoint Analysis

Objective 2

Anxiety and depression outcomes will be captured if occurring prior to, or within two years of, an individuals' study index date. Binary outcome logistic regression model outputs will be used to compare the burden of anxiety and depression in vitiligo cases compared to matched controls. Furthermore, additional analyses for new onset anxiety and depression outcomes will be conducted, excluding people with a previous record of the respective mental health condition. Anxiety and depression outcomes will be defined by the first occurrence of a relevant code in the primary care record up to two years post index-date. Cox proportional hazards regression will be used to estimate the excess risk of anxiety and depression outcomes in vitiligo cases versus controls. Results will be described as hazard ratios.

Objective 3

Parasuicide/suicide attempts will be defined by the first occurrence of a relevant code in the primary care record up to two years post index-date. People with a previous record of parasuicide/suicide attempt will be excluded from the calculations. Cox proportional hazards regression will be used to estimate the excess risk of parasuicide/suicide attempts in vitiligo cases versus matched controls. Results will be described as hazard ratios.

Adjustment disorder and sleep disturbance will be defined by the first occurrence of a relevant code in the primary care record up to two years post index-date. People with a previous record of the adjustment disorder will be excluded from the from the adjustment disorder endpoint analysis. Cox proportional hazards regression will be used to estimate the excess risk of the relevant condition in vitiligo cases versus matched controls. Results will be described as hazard ratios.

Objective 4

Dermatology referral and mental health referral or reviews will be defined by the first occurrence of a relevant code in the primary care record up to two years post index date. Cox proportional hazards regression will be used to estimate the excess risk of these outcomes in vitiligo cases versus matched controls.

For primary care encounters reviews, defined as a rate of encounters within two years after the index date, will be compared using generalised linear models with time-at-risk as an offset. Results will be described as incidence rate ratios.

Objective 5

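### Sleep disturbance in Objective 3 has no stated rule for pre-index codes, so its hazard ratio covers new and repeat codes and is not comparable with the four new-onset hazard ratios beside it

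*Combined protocol and SAP*

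**What the plan says.** In section 8.3, Objective 3, one sentence defines two endpoints: "Adjustment disorder and sleep disturbance will be defined by the first occurrence of a relevant code in the primary care record", with a window of two years after index. One model sentence also serves both: "Cox proportional hazards regression will be used to estimate the excess risk of the relevant condition in vitiligo cases versus matched controls". Between them stands an exclusion that names only one of the two: "People with a previous record of the adjustment disorder will be excluded from the from the adjustment disorder endpoint analysis".

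The neighbouring analyses each state a rule. For parasuicide: "People with a previous record of parasuicide/suicide attempt will be excluded from the calculations". For the additional new-onset anxiety and depression analyses under Objective 2, the rule is "excluding people with a previous record of the respective mental health condition". The separate logistic analysis of anxiety and depression burden counts earlier history on purpose: "Anxiety and depression outcomes will be captured if occurring prior to, or within two years of, an individuals' study index date". It is not an onset analysis and so is not a counterexample.

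Table 2 in section 4.5 gives only a window for the Objective 3 outcomes: "Other mental health condition outcomes will be assessed up to two years post-vitiligo diagnosis". It does not mention earlier sleep codes.

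**The concern.** Five diagnosed conditions in Objectives 2 and 3 get a Cox hazard ratio for cases against matched controls. Four are restricted to people with no earlier record of the condition. The fifth, sleep disturbance, is not, and no reason is given. A reader of the results would naturally set the five hazard ratios side by side, although one of them answers a different question.

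Two things are at stake. First, the all-comers ratio averages the association in people with and without earlier sleep codes, weighted by how many events each group contributes. Objective 3 compares sociodemographic subgroups, and that weighting may differ between them. Second, if cases and controls differ in pre-index sleep history, that difference alone can produce a ratio away from 1.

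**Working it through.** The plan gives no sleep-disturbance rate, event count, hazard ratio or power, so there is no figure to reproduce. The check is textual, followed by an illustration on assumed inputs.

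**Step 1: rule for prior records in each Cox analysis (section 8.3).**

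| Endpoint | Prior cases excluded? |
|---|---|
| Anxiety, new onset | Yes |
| Depression, new onset | Yes |
| Parasuicide/suicide attempt | Yes |
| Adjustment disorder | Yes |
| Sleep disturbance | None stated |

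Four of five state an exclusion.

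**Step 2: does anything else handle earlier sleep codes?**
- Matching (7.3) is on age, sex, ethnicity and deprivation within practice. Sleep history is not included.
- The fullest adjustment set (8.1) has age, sex, BMI, smoking, alcohol and listed physical comorbidities plus dementia. It has no prior sleep or mental health history.
- The sensitivity analyses (8.4) concern controls who do not attend, a four-year outcome period and missing ethnicity.

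None of these addresses the point.

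**Step 3: illustration.** All inputs are assumed. Two-year risk ratios stand in for hazard ratios. Let q1 and q0 be the proportions of cases and controls with a prior code, r the two-year recurrence risk and n the two-year new-onset risk in controls. Let h be the ratio in people without a prior code and g the ratio in people with one.

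Mixed ratio = [q1·r·g + (1 − q1)·n·h] / [q0·r + (1 − q0)·n]

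Take r = 0.25, n = 0.03.

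- *Equal history, no effect on recurrence* (q1 = q0 = 0.20, h = 1.30, g = 1): cases 0.20×0.25 + 0.80×0.03×1.30 = 0.0812; controls 0.20×0.25 + 0.80×0.03 = 0.074; ratio **1.10**.
- *Equal history, same effect on recurrence* (g = 1.30): (0.05×1.30 + 0.024×1.30)/0.074 = **1.30**, the new-onset ratio unchanged.
- *No effect in either group, unequal history* (q1 = 0.20, q0 = 0.15): cases 0.074; controls 0.15×0.25 + 0.85×0.03 = 0.063; ratio **1.17**.

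**Step 4: range over other assumed inputs.** Put k = r/n, the recurrence risk relative to new onset. Dividing through by n gives [(1 − q1)·h + q1·k·g] / [(1 − q0) + q0·k].

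- h = g = 1, q0 = 10%, q1 = 15%: k = 3 gives 1.30/1.20 = 1.08; k = 10 gives 2.35/1.90 = 1.24. Here the mixed ratio is above the new-onset ratio of 1.
- h = 1.5, g = 1, q0 = q1 = 10%: k = 3 gives 1.65/1.20 = 1.38; k = 10 gives 2.35/1.90 = 1.24. Here it is below the new-onset ratio of 1.5.
- Share of control events from people with a prior code, q0·k/[(1 − q0) + q0·k]: from 0.15/1.10 = 14% (q0 = 5%, k = 3) to 2.0/2.8 = 71% (q0 = 20%, k = 10).

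**Step 5: subgroups.** With r = 0.25, n = 0.03, h = 1.30, g = 1 and equal history in cases and controls, a subgroup with 5% prior codes shows 0.04955/0.041 = 1.21. One with 30% shows 0.1023/0.096 = 1.07. The new-onset ratio is the same in both. With g = 1.30 both would show 1.30.

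**The case against.** The strongest reply is that the omission may be deliberate and harmless. Sleep problems recur. The exclusion is expressly confined to adjustment disorder in a paragraph that covers both conditions. The Cox outcomes in Objectives 4 and 5 (referrals, unemployment, time off work) also use the first post-index code with no prior-record exclusion. Objective 3 in section 4.3.2 speaks of association and does not say new onset.

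Much of this stands. Time from index to first post-index code, in everyone, is a well-defined single-event Cox outcome. It is a different target from new onset and is not an invalid one. That the plan retains prior sleep codes is inferred from silence, and a drafting slip is also possible. The parallel with Objectives 4 and 5 is only partial, because those are service and work events. For every other diagnosed condition analysed by Cox, the plan excludes prior cases.

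Four stronger inferences are tempting, and the documents do not support them:
- *That keeping prior codes requires a recurrent-event definition.* Such methods are needed only if several events per person are counted.
- *That people with earlier codes have events before time zero.* The wording on first occurrence could be stretched to mean first ever. The two-year post-index window in sections 8.3 and 4.5 makes the first code after index the ordinary reading.
- *That repeat codes will swamp new ones or pull the ratio towards 1.* No sleep prevalence or recurrence figure is given, and attenuation depends on the effect among people with prior codes.
- *That prior sleep history is known to differ between arms or subgroups.* Section 3.1 reports excess mental health burden in vitiligo, which makes a difference between cases and controls plausible. It gives no sleep figure, and none is given by subgroup.

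**Conclusion.** The point holds as a gap in specification and comparability. As written, the sleep-disturbance hazard ratio is for any post-index code. It is unprotected against unequal pre-index sleep history and is not on the same footing as the four new-onset hazard ratios.

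The direction and size of any difference from the new-onset ratio cannot be determined from the documents. In the illustration, a new-onset ratio of 1.30 appears as anything from 1.10 to 1.30, depending solely on whether vitiligo affects recurrence. A ratio of 1 in both groups appears as 1.17 when prior records are 20% in cases and 15% in controls. On the risk-ratio scale used there, nothing is distorted if prior prevalence is the same in cases and controls and the effect is the same with and without a prior code. The point affects one component of one secondary objective. The lifetime-risk analysis is untouched.

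**What to change.** In section 8.3, Objective 3:
- Add a new-onset sleep-disturbance Cox model that excludes people with a sleep-disturbance code before index, in the same way as for adjustment disorder.
- If the all-comers analysis is kept, say so, stratify it by prior sleep record and label its hazard ratio as any post-index code, new or repeat.
- Present only the new-onset model alongside the anxiety, depression, parasuicide and adjustment disorder hazard ratios.

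The data are already in the primary care record. The cost is about a sentence of text, one extra model and fewer events in the new-onset analysis, which will be felt most in the smaller subgroups. Section 9 anticipates low numbers for adjustment disorder and parasuicide/suicide but does not list sleep disturbance.

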4.3 Secondary Objectives

4.3.1 Objective 2

Describe any disparities in the burden of mental health outcomes, including depression and anxiety in people with vitiligo across sociodemographic subgroups.

4.3.2 Objective 3

Describe any disparities in the association of vitiligo with parasuicide/suicide attempts, adjustment disorder and sleep disturbances associated with vitiligo across sociodemographic subgroups.

4.3.3 Objective 4

Describe any disparities in vitiligo-associated healthcare utilisation across sociodemographic subgroups.

4.3.4 Objective 5

Describe any disparities in vitiligo-associated work impact (time off work for illness and unemployment) across sociodemographic subgroups.

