Only cases and matched controls aged 18-65 will be considered for this analysis. Work impact outcomes (unemployment and time off work for illness) will be defined by the first occurrence of a relevant code in primary care record up to two years post index date. Cox proportional hazards regression will be used to estimate the excess risk of these outcomes in vitiligo cases versus matched controls. Results will be described as hazard ratios.

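### Objective 5 takes the first unemployment or sick-note code after index without accounting for earlier codes, so repeat codes can distort the work-impact hazard ratios by amounts that differ between subgroups

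*Combined protocol and SAP*

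**What the plan says.** The aim of Objective 5 in section 4.3 is: "Describe any disparities in vitiligo-associated work impact (time off work for illness and unemployment) across sociodemographic subgroups".

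Section 4.5 (Table 2) sets the two endpoints. For unemployment, "Unemployment in the two years post-vitiligo diagnosis will be identified using Read codes relating to unemployment recorded in the primary care record", or by the issue of an IB113 or ESA113 form. For sick leave, "Time off work in the two years post-vitiligo diagnosis will be indicated by the issuing of Med 3 certification from primary care".

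Section 8.3 then gives the analysis. The one restriction on who enters it is an age limit: "Only cases and matched controls aged 18-65 will be considered for this analysis". The events are set out as follows: "Work impact outcomes (unemployment and time off work for illness) will be defined by the first occurrence of a relevant code" up to two years after index. The model is named last: "Cox proportional hazards regression will be used to estimate the excess risk of these outcomes in vitiligo cases versus matched controls".

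Elsewhere in section 8.3 some time-to-first-code outcomes do carry a rule for earlier records. For Objective 2, "additional analyses for new onset anxiety and depression outcomes will be conducted, excluding people with a previous record of the respective mental health condition". For Objective 3, "People with a previous record of parasuicide/suicide attempt will be excluded from the calculations", and adjustment disorder has the same kind of exclusion. Sleep disturbance, dermatology referral and mental health referral have none.

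**The concern.** Unemployment is a state that can persist, and Med 3 certificates can be issued repeatedly. A code after index may therefore record a situation that began before the vitiligo diagnosis. As written, the model mixes two kinds of event: new work loss, and repeat coding in people already unemployed or signed off.

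The hazard ratio is then a blend of the two, and the share of repeat codes sets the weights. If that share varies between deprivation quintiles, age bands or ethnic groups, the blend varies as well. A subgroup difference in the hazard ratio could then partly reflect who already had a code, and not how vitiligo affects work. Since Objective 5 is about subgroup differences, this bears directly on how its results can be read.

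**Working it through.** **Step 1: is there a rule anywhere else?**

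- Exclusion criteria (7.2): nothing on earlier work codes.
- Matching (7.3): age, sex, ethnicity, deprivation and practice. Prior work status is not a factor.
- Adjustment sets (8.1): demographic, lifestyle and comorbidity terms. No prior unemployment or sick-note term.
- Sensitivity analyses (8.4): controls who attend the practice, a four-year window, and missing ethnicity. None deals with earlier codes.

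The reference to a first code does not settle it. The same phrase is used for new-onset anxiety and depression, parasuicide and adjustment disorder, and there the plan adds an exclusion.

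**Step 2: the mechanism.** The plan gives no figure for Objective 5, so there is nothing to reproduce. Every input below is an assumption.

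Let p be the share with a prior code, r the two-year risk of a repeat code, q the two-year risk of a new code, R the case-control ratio for new codes and k the ratio among prior-code holders. With p equal in cases and controls:

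observed risk ratio = [p·r·k + (1−p)·q·R] / [p·r + (1−p)·q]

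Take r = 30%, q = 2%, R = 1.30. With k = 1.00:

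- p = 3%: (0.009 + 0.0194×1.3) / 0.0284 = 1.20
- p = 10%: (0.030 + 0.018×1.3) / 0.048 = 1.11
- p = 20%: (0.060 + 0.016×1.3) / 0.076 = 1.06

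With k = 1.15 the first term of each numerator is multiplied by 1.15. For p = 20%: (0.069 + 0.0208) / 0.076 = 1.18.

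For the last column, set R = k = 1 and give cases 1.2 times as many prior codes. For p = 20%: (0.24×0.30 + 0.76×0.02) / 0.076 = 0.0872 / 0.076 = 1.15.

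| Prior share p | k = 1.00 | k = 1.15 | k = 1.30 | No effect, cases hold 1.2 times the prior codes |
|---|---|---|---|---|
| 3% | 1.20 | 1.25 | 1.30 | 1.06 |
| 10% | 1.11 | 1.21 | 1.30 | 1.12 |
| 20% | 1.06 | 1.18 | 1.30 | 1.15 |

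The new-onset risk matters too. With k = 1.00, p = 20% and q = 6%: (0.060 + 0.048×1.3) / 0.108 = 1.13, not 1.06.

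**Step 3: the same on the hazard-ratio scale.** The plan uses Cox models, so the large-sample Cox hazard ratio was computed for one case to four controls over two years. Assumed hazards were 0.3-0.6 per year for repeat codes and 0.03-0.05 for new codes in controls. Repeat coding has ratio 1.0 between cases and controls.

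| Scenario | p = 5% | p = 15% | p = 30% |
|---|---|---|---|
| True new-onset HR 1.25 | 1.16-1.20 | 1.08-1.14 | 1.04-1.09 |
| True new-onset HR 1.50 | 1.31-1.40 | 1.17-1.28 | 1.09-1.17 |
| True HR 1.00, prior codes balanced | 1.00 | 1.00 | 1.00 |
| True HR 1.00, cases hold 1.2 times the prior codes | 1.03-1.08 | 1.08-1.14 | 1.12-1.18 |

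Removing prior-code holders returns the true value in every cell.

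**Step 4: the other reading.** If the plan means the first code ever, prior-code holders stay in the risk set but cannot have an event. With a true HR of 1.5 and a new-code hazard of 0.05, the hazard ratio barely moves (1.498 at p = 5%, 1.485 at p = 40%). The two-year risk in controls, however, falls from 9.0% to 5.7%. The text needs clarifying on either reading.

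**The case against.** **The endpoint is not labelled new onset.** Section 4.5 defines unemployment or certificate issue within two years of diagnosis, and section 4.3 speaks of work impact. Any certified absence after diagnosis is a legitimate measure of burden, above all for Med 3 certificates, which recur. This stands. It is why the all-comers analysis should be kept and why the point is stronger for unemployment. It does not remove the need to say which quantity is being estimated.

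**Matching protects the comparison.** Cases and controls share age, sex, ethnicity, deprivation and practice. If prior codes are balanced and vitiligo has no effect, the ratio is 1.00 in every subgroup. This also stands. But matching on deprivation does not make prior-code prevalence equal across quintiles, and prior work status is not matched.

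**The limitations section covers it.** Section 9 says that outcomes cannot be tied to vitiligo and that causal interpretation is not possible. That tempers how the results will be read. It does not mention earlier codes, and it still interprets disparities on the assumption that outcomes are related to vitiligo.

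**Stronger readings that a reader might infer.** One is that Objective 5 alone lacks a prior-record rule. It does not: sleep disturbance and both referral outcomes lack one too, and Objective 2 opens with an analysis that deliberately includes prior records. Another is that repeat codes in themselves register as excess risk after vitiligo. When balanced, they add equally to both groups and pull the ratio toward the repeat-code ratio. Excess arises only if cases hold more prior codes.

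**Conclusion.** The gap is real: earlier unemployment and sick-note codes are not excluded, stratified by or adjusted for in Objective 5. The distortion is conditional. A false subgroup difference needs prior-code prevalence that varies between subgroups. It also needs either a vitiligo effect that is larger for new than for repeat codes, or more prior codes in cases than in controls. The first route dilutes and the second inflates, so the direction cannot be stated in advance.

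A reader might infer from the 1.20-to-1.06 gradient that a false deprivation gradient of that size is to be expected. The documents do not support this. They give no prior-code prevalence, repeat rate or work-event rate. The gradient also rests on no effect among prior-code holders and equal onset in every group. At a repeat ratio of 1.15 it shrinks to 1.25 versus 1.18, and at 1.30 the risk-ratio gradient disappears. The size is unknown.

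For a secondary, descriptive objective, this is a cheap improvement.

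**What to change.** In section 8.3, Objective 5:

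- State whether the event is the first code after index or the first code ever.
- Add a new-onset unemployment model that excludes cases and controls with an unemployment, IB113 or ESA113 code in a pre-specified look-back before index. An unlimited look-back would also remove people who have since returned to work.
- Stratify the time-off-work model by Med 3 issue in a pre-specified look-back, for example 12 months (the documents give no basis for a particular length). Show the hazard ratio within each stratum, because one value pooled over strata would still average the two.
- Report both beside the all-comers results, by subgroup, with the share of cases and controls holding a prior code.

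This mirrors Objective 2, which pairs an analysis including prior records with a new-onset one. It uses data already in the record and costs SAP wording and a re-run. The downsides are fewer events, felt most in small subgroups, and some residual misclassification because employment status is likely to be incompletely coded in primary care.
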